### **8.2.1 Overdose**

An overdose is defined as the accidental or intentional administration of any dose of the product that is considered both excessive and medically important. Any instance of overdose (suspected or confirmed and irrespective of whether or not it involved rimegepant (BHV-3000) must be communicated to Biohaven or a specified designee within 24 hours and be fully documented as an SAE. Details of any signs or symptoms and their management should be recorded including details of any antidote(s) administered.

### **8.2.2 Pregnancy**

If following initiation of the investigational product, it is subsequently discovered that a study patient is pregnant or may have been pregnant at the time of the investigational product exposure, including during at least 6 half-lives after the product administration, the investigational product will be permanently discontinued in an appropriate manner (i.e., dose tapering if necessary for patient safety). Protocol-required procedures for the study will be discontinued and the follow up must be performed on the patient unless contraindicated by the pregnancy (i.e., x-ray studies). Other appropriate pregnancy follow-up procedures should be considered if indicated.

Sites should instruct patients to contact the investigator if they become pregnant during the course of the study. The investigator must immediately notify PPD of the event within 24 hours of the Investigator becoming aware of the information. The site must complete a Pregnancy Report Form. Follow up information regarding the course of the pregnancy, including perinatal and neonatal outcome and, where applicable offspring information must also be reported on a Pregnancy Report Form.

Any pregnancy that occurs in a female partner of a male study participant should be reported to PPD.

### **8.2.3 Potential Drug Induced Liver Injury (DILI)**

Wherever possible, timely confirmation of the initial liver-related laboratory abnormalities should occur prior to the reporting of a potential DILI event. All occurrences of potential DILIs, meeting the defined criteria, must be reported as SAEs as per Section 8.2.

Potential drug induced liver injury is defined as:

- Aminotransferases (AT) (ALT or AST) elevation > 3 times the upper limit of normal (ULN);

*AND*

- Total bilirubin (TBL) > 2 times ULN, without initial findings of cholestasis (elevated serum alkaline phosphatase);

*AND*

- No other immediately apparent possible causes of AT elevation and hyperbilirubinemia, including but not limited to, viral hepatitis, pre-existing chronic or acute liver disease, or the administration of other drug(s) known to be hepatotoxic.

If any potential DILI is identified and meets the criteria above, the Biohaven Medical Monitor should immediately be contacted for further instruction on dosing adjustments and whether the patient must discontinue from the trial and appropriate follow up requirements.

### **8.3 Non-Serious Adverse Events**

A non-serious adverse event is an AE not classified as serious.

#### ***8.3.1 Collection and Reporting of Non-Serious Adverse Events***

The collection of non-serious AE information should begin at the Baseline visit. Non-serious AE information should also be collected from any observational period intended to establish a baseline status for a subject.

Non-serious adverse events should be followed until conclusion or stabilization, or reported as SAEs if they become serious. Follow-up is also required for non-serious AEs that cause interruption or discontinuation of study drug/medication or those that are present at the end of study treatment.

#### ***8.3.2 Laboratory Test Abnormalities***

The following laboratory test abnormalities should be captured on the non-serious AE CRF page or SAE Report Form (paper or electronic) as appropriate:

1. Any laboratory test result that is clinically significant or meets the definition of an SAE;
2. Any laboratory abnormality that required the subject to have the study drug/medication discontinued or interrupted;
3. Any laboratory abnormality that required the subject to receive specific corrective therapy.

## **9 STATISTICS**

Detailed plans for analysis will be summarized in a separate Statistical Analysis Plan document, to be written and approved prior to database unblinding. A summary of statistical aspects of the design and intended analysis is provided here.

### **9.1 General Procedures**

Categorical variables are tabulated with counts and percentages. Continuous variables are summarized with univariate statistics (e.g., n, mean, standard error, median, minimum and maximum).

For the calculation of descriptive statistics of observed data, subjects must have a baseline value to be evaluable for endpoints based on values and changes from baseline over time.

Tabulations of the following endpoints present the number of unique subjects with an event: protocol deviations; interruptions of study therapy; non-study drug/medications; adverse events; and laboratory abnormalities. Thus, for these endpoints, multiple occurrences of the same event are counted only once per subject within the period.

### **9.2 Sample Size**

The sample size for this study will be approximately 60 randomized patients. Approximately 120 patients will be screened, assuming no more than 50 percent of patients will be ineligible for randomization.

The calculation for the sample size is based on a paired t-test crossover design, assuming a low correlation ( $r = 0.2$ ) between the active and placebo response to treatment. Assuming a paired difference standard deviation of 3.8, 60 randomized patients will provide  $>90\%$  power to detect a 2-point difference between rimegepant and placebo using a two-sided significance level of 0.05 and a 20% dropout rate with no imputation.

### **9.3 Populations for Analysis**

The following analysis sets are defined for this protocol:

- Enrolled subjects: Patients who signed an informed consent form and were assigned a Patient Identification number (PID)
- Randomized subjects: Enrolled subjects who received a treatment assignment from the Interactive Web Response System (IWRS) (rimegepant or placebo).
- Treated subjects: Enrolled subjects who received at least 1 dose of blinded study therapy (rimegepant or placebo).

- **Modified Intent to Treat (mITT) subjects:** Randomized subjects that received at least one dose of study therapy and provided a baseline and at least one post-baseline efficacy assessment in each sequence

## **9.4 Statistical Methods**

### **9.4.1 Demographic and Baseline Characteristics**

Tabulations of demographic and baseline characteristics will be summarized for all treated subjects. A separate set of tabulations will be made for subjects enrolled but not randomized.

### **9.4.2 Primary Endpoint(s)**

The primary endpoint will estimate the effect of rimegepant relative to placebo over 2 weeks of treatment when added to a standard of care therapy, and regardless of the effect of other concomitant medication. The pain score will be the average of the daily 11-point NPRS recorded within each period using the mITT population. This treatment effect will be summarized as the difference in the average daily score in total NPRS between rimegepant and placebo.

The treatment comparison of rimegepant versus placebo will use a two-sided alpha level of 0.05 and a Mixed Model for Repeated Measures (MMRM) that will include fixed effect factors for treatment group, randomization strata (typical/atypical) and sequence, with baseline NPRS as a covariate and subject as a random factor. MMRM-based estimates with corresponding SD, 95% CI, and p-value from MMRM will also be presented.

Observed values and changes from baseline in NPRS will also be summarized using descriptive statistics over time by treatment group.

### **9.4.3 Secondary Endpoint(s)**

Continuous secondary, change-from-baseline efficacy endpoints (Penn Facial Pain Scale, Pain Disability Index , Worst pain episode using the NPRS) will be analyzed using the same methodology as the primary endpoint. As the PGI-C, does not have a baseline value, the summary will be computed using an analysis of variance, that will include fixed effect factors for treatment group, randomization strata (typical/atypical) and sequence. Achievement of at least a 2-point reduction in NPRS will be analyzed using logistic regression, that will include terms for treatment group, randomization strata (typical/atypical), sequence, and baseline NPRS.

### **9.4.4 Adjustment for Multiplicity**

Type 1 error will be controlled for the primary and secondary efficacy endpoints by testing them with a gate-keeping procedure. The primary endpoint will be tested at a two-sided alpha level of 0.05. If this test is significant, then the secondary efficacy endpoints will be tested using Hochberg's procedure. If the test of the primary endpoint is not significant, then the unadjusted p-values for the secondary endpoints will be presented only for descriptive purposes, and no conclusions will be drawn from this result

#### **9.4.6 Analysis of Safety**

The investigators determine the intensity of AEs and the relationship of AEs to study therapy. The investigators' terms are coded and grouped by system organ class using the latest version of the Medical Dictionary for Regulatory Activities (MedDRA) available. AEs are presented by system organ class and preferred term, ordered by the overall frequency of events. If a subject had an adverse event with different intensities over time, then only the greatest intensity is reported.

AEs are tabulated in all treated subjects. SAEs occurring in subjects enrolled but not treated are listed. Deaths are listed for enrolled subjects without regard to onset.

The frequencies of the following safety events are summarized by treatment and overall: SAEs; all AEs, nonserious AEs, AEs by intensity; AEs by relatedness and clinically relevant laboratory abnormalities.

Graphical and tabular displays of on-treatment liver function test results are provided.

#### **9.5 Schedule of Analyses**

The final analysis of the Double-blind Treatment Phase will occur after the last subject randomized has completed this phase of the study or discontinues from the Double-blind Treatment Phase. The study will be unblinded and analyses will summarize all efficacy, safety, laboratory and other data collected throughout the double-blind phase of study.

A final analysis of the study will be completed after the last subject has completed their last study visit of the Open-Label Extension Phase of the study. These analyses will summarize all efficacy, safety, laboratory and other data collected throughout the Open-Label Extension Phase of the study. In addition throughout the study, data may be locked, analyses conducted, and reports produced as required to support safety monitoring or regulatory requirements.

## 10 ETHICS AND RESPONSIBILITIES

### 10.1 Good Clinical Practice

This study will be conducted in compliance with the protocol, Good Clinical Practice (GCP), Good Laboratory Practice (GLP) and all applicable regulations, including the Federal Food, Drug and Cosmetic Act, U.S. applicable Code of Federal Regulations (title 21), any IEC requirements relative to clinical studies. The study will also be conducted in compliance with the recommendations laid down in the most recent version of the Declaration of Helsinki, with the exception that registration of such Phase 1 trials in a publicly accessible database is not mandatory.

This study will be conducted in compliance with the protocol. The protocol and any amendments and the patient informed consent will receive Institutional Review Board/Independent Ethics Committee (IRB/IEC) approval/favorable opinion prior to initiation of the study.

All serious breaches must be reported to Biohaven (or designee) immediately. A Serious breach is a breach of the conditions and principles of GCP in connection with the study or protocol, which is likely to affect, to a significant degree, the safety or physical or mental integrity of the patients of the study or the scientific value of the study.

Study personnel involved in conducting this study will be qualified by education, training, and experience to perform their respective task(s).

This study will not use the services of study personnel where sanctions have been invoked or where there has been scientific misconduct or fraud (e.g., loss of medical licensure, debarment).

### 10.2 Data and Safety Monitoring Committee

This study will not make use of a Data Safety Monitoring Committee (DMC). The study drug/medication BHV-3000 has been tested and found to be well tolerated. Safety will be closely monitored via the sites and procedures for unblinding in cases of emergency will be followed.

### 10.3 Institutional Review Board/Independent Ethics Committee

The Investigators agree to provide the IRB/IEC with all appropriate documents, including a copy of the protocol/amendments, ICFs, advertising text (if any), Investigator's brochure (if any) and any other written information provided to study subjects. The trial will not begin until the Investigators have obtained the IRB/IEC favorable written approvals for the above-mentioned study documents. A properly executed written ICF shall be read, signed, and dated by each subject prior to entering the trial or prior to performing any study procedure. The original signed and dated ICF will be kept at the Investigator site and a copy will be given to the subject.

In the event that the protocol is amended, the revised protocol must be approved by the IRB/IEC prior to its implementation, unless the changes involve only logistical or administrative aspects of the trial. If a revised ICF is introduced during the study, each subject's further consent must be

obtained. The new version of the ICF must be approved by the IRB/IEC, prior to subsequently obtaining each subject's consent.

The Principal investigator and the Sponsor's representative must sign the protocol and its amendments (if any) before initiating the study.

It is the Sponsor's responsibility to submit the protocol and its amendments (if any), and the ICFs to regulatory authorities when necessary.

#### **10.4 Informed Consent**

Investigators must ensure that patients, or, in those situations where consent cannot be given by patients, their legally acceptable representatives, are clearly and fully informed about the purpose, potential risks, and other critical issues regarding clinical studies in which they volunteer to participate.

Biohaven (or designee) will provide the investigator with an appropriate (i.e., Global or Local) sample informed consent form which will include all elements required by ICH, GCP and applicable regulatory requirements. The sample informed consent form will adhere to the ethical principles that have their origin in the Declaration of Helsinki.

Before the potential subject has undergone any study-related screening procedures, the nature of the study and the potential risks associated with it will be explained to the subject, and the subject will be given an opportunity to ask questions to his or her satisfaction. After the questions are answered, but before proceeding further, the subject must read and sign a written informed consent form. This signed informed consent form will be reviewed and approved by an IRB/IEC, revisions to the protocol and informed consent form will be reviewed and approved by the IRB/IEC, a copy retained in the Study Master File, and the date and time the subject signed the form will be entered in his or her CRF. The subject will be provided with a copy of his or her signed and dated informed consent form.

If informed consent is initially given by a patient's legal guardian or legally acceptable representative, and the patient subsequently becomes capable of making and communicating their informed consent during the study, then the consent must additionally be obtained from the patient.

The informed consent form must also include a statement that Biohaven and its representatives and regulatory authorities may have direct access to patient records.

The rights, safety, and well-being of study patients are the most important considerations and should prevail over interests of science and society.

#### **10.5 Case Report Forms**

An investigator is required to prepare and maintain adequate and accurate case histories designed to record all observations and other data pertinent to the investigation of each study patient. Data reported on the CRF that are derived from source documents must be consistent with the source documents or the discrepancies must be explained.

Paper CRFs will be prepared for all data collections fields.

The confidentiality of records that could identify patients must be protected, respecting the privacy and confidentiality rules in accordance with the applicable regulatory requirement(s).

The investigator must retain a copy of the CRFs including records of changes and corrections.

## 11 RECORDS AND MANAGEMENT RETENTION

In accordance with the principles of GCP and GLP, the study may be inspected by regulatory authorities, the Sponsor and CRO. The Sponsor is entitled to access information about the status of the study and to review the original documents of the study.

The investigator must retain all study records and source documents for the maximum required by the applicable regulations and guidelines, or institution procedures or for the period of time specified by the sponsor, whichever is longer. The investigator must contact the Sponsor prior to destroying any records associated with this study.

Biohaven will notify the investigators when the study files for this study are no longer needed.

If the investigator withdraws from the study (i.e., retirement, relocation), the records shall be transferred to a mutually agreed upon designee. Notice of such transfer will be given in writing to Biohaven.

It is the responsibility of the investigator to ensure that the current disposition record of investigational product (those supplied by the sponsor) is maintained at each study site where the study drug/medication is inventoried and dispensed. Records or logs must comply with applicable regulations and guidelines and should include:

1. Amount of study drug/medication received and placed in storage area;
2. Label ID number or batch number or Kit number as specified for the protocol;
3. Amount dispensed to and returned from each patient;
4. Amount transferred to another area or site for dispensing or storage if applicable;
5. Amount of drug lost or wasted;
6. Amount destroyed at the site if applicable;
7. Amount returned to sponsor, if applicable;
8. Retained samples for bioavailability/bioequivalence, if applicable;
9. Record of dates and initials of personnel responsible for IM dispensing and accountability.

### 11.1 Source Documentation

An investigator is required to prepare and maintain adequate and accurate case histories designed to record all observations and other data pertinent for all subjects on study.

If source documents are created to support the collection of study information, this must be retained with the other pertinent medical record for each patient for verification of data points, unless otherwise instructed by the Sponsor or designee to enter data directly on the CRF.

## **11.2 Study Files and Record Retention**

The CRO will utilize the Sponsor's Electronic Trial Master File (eTMF) for the purposes of this study. The Sponsor does not require original documents that have already been scanned and entered into the eTMF system be forwarded to the Sponsor. Any original documents (i.e. 1572, signed financial disclosure, signed ICF, etc.) will be retained in the regulatory binder at the study site. The CRO will do a final TMF reconciliation to ensure all study files and regulatory documents have been correctly uploaded to the TMF prior to the close or termination of the study. Any materials or documents to support the clinical trial outside of the eTMF (i.e. rater training tapes) should be maintained by the CRO. The Sponsor will be contacted to determine whether the study documents/materials that are retained outside of the TMF will be forwarded to the Sponsor, destroyed or kept at CRO or at another facility for a longer period of time at the Sponsor's expense.

## **12 AMENDMENTS**

Protocol modifications, except those intended to reduce immediate risk to study subjects, may be made only by Biohaven. A protocol change intended to eliminate an apparent immediate hazard to subjects may be implemented immediately, provided the IRB/IEC is notified within 5 days.

Any permanent change to the protocol must be handled as a protocol amendment. The written amendment must be submitted to the IRB/IEC and the investigator must await approval before implementing the changes. Biohaven will submit protocol amendments to the appropriate regulatory authorities for approval.

If in the judgment of the IRB/IEC, the investigator, and/or Biohaven, the amendment to the protocol substantially changes the study design and/or increases the potential risk to the subject and/or has an impact on the subject's involvement as a study participant, the currently approved written informed consent form will require similar modification. In such cases, informed consent will be renewed for subjects enrolled in the study before continued participation.

## **13 STUDY REPORT AND PUBLICATIONS**

Biohaven is responsible for preparing and providing the appropriate regulatory authorities with clinical study reports according to the applicable regulatory requirements.

The publication policy of Biohaven is discussed in the investigator's Clinical Research Agreement.

## **14 STUDY DISCONTINUATION**

Both Biohaven and the Principal Investigator reserve the right to terminate the study at the investigator's site at any time. Should this be necessary, Biohaven or a specified designee will inform the appropriate regulatory authorities of the termination of the study and the reasons for its termination, and the Principal Investigator will inform the IRB/IEC of the same. In terminating the study, Biohaven and the Principal Investigator will assure that adequate consideration is given to the protection of the subjects' interests.

## **15 CONFIDENTIALITY**

All information generated in this study is considered highly confidential and must not be disclosed to any person or entity not directly involved with the study unless prior written consent is gained from Biohaven and its authorized representatives are allowed full access to the records.

Identification of subjects and CRFs shall be by initials, screening and treatment numbers only. If required, the subject's full name may be made known to an authorized regulatory agency or other authorized official.

## **Appendix 2: Inhibitors and Inducers of CYP3A4 and Inhibitors of P-glycoprotein (Not all-inclusive)**

The following medications and medication combinations are some of the moderate to strong inhibitors of CYP3A4 and strong P-glycoprotein (p-gp). This list should not be considered all-inclusive. As described in the study protocol, concomitant use of moderate to strong CYP3A4 inhibitors is prohibited. Individual drug labels should be reviewed for specific information on propensity to cause moderate to strong inhibition of the CYP3A4 enzyme or strong inhibition of the p-gp transporters for a specific given compound.

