#### **4.4 Prohibited Concomitant Medication**

The below medications are prohibited prior to randomization and during the course of this study or as specified.

1. St. John's Wort should not be taken 14 days prior to randomization and throughout the study.
2. Barbiturate-containing products (e.g. Fioricet, Fiorinal, butalbital, phenobarbital) should not be taken 14 days prior to randomization and throughout the study.
3. Modafinil (PROVIGIL®) should not be taken 14 days prior to randomization and throughout the study.
4. Butterbur root or extracts should not be taken 14 days prior to randomization and throughout the study.
5. History of use of ergotamine medications on greater than/equal 10 days per month on a regular basis for greater than/equal 3 months.
6. Use of narcotic medication, such as opioids (e.g. morphine, codeine, oxycodone and hydrocodone) for at least 2 days prior to randomization.
7. Use of all acetaminophen or acetaminophen containing products must be discontinued at least 2 days prior to randomization (acetaminophen < 1000 mg/day is allowed as rescue medication, see Section 5.3.5). During the screening phase (14 to 30 days) use of acetaminophen or acetaminophen containing products at daily dosing levels of greater than 1000 mg/day is prohibited.
8. Use of marijuana is prohibited during the study.
9. Muscle relaxants are prohibited during the study. The use of baclofen is permitted, provided that patients are on stable dosing for at least 8 weeks prior to their randomization visit.
10. Concomitant use of strong CYP3A4 inhibitors with rimegepant is prohibited during the study. If use of a strong CYP3A4 inhibitor is required, such as use of HIV Protease Inhibitors, Hepatitis C protease inhibitors, certain azole antifungals, or clarithromycin, dosing with rimegepant should be stopped. Please see section 17, [Appendix 2](#).

11. Concomitant use of strong CYP3A4 inducers with rimegepant is prohibited during the study. Therefore, the use of carbamazepine during this study will be prohibited. However, patients taking oxcarbazepine for the treatment of their trigeminal neuralgia may continue with their current therapy, provided they have been on stable dosing for at least 4 weeks prior to their randomization visit. Patients on carbamazepine may be transitioned to oxcarbazepine. Similarly, these patients must be on stable doses of oxcarbazepine for at least 4 weeks prior to the randomization visit. Please see section [17, Appendix 2](#).

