### **Moderate CYP3A4 inhibitors**

Amprenavir, aprepitant, casopitant, cimetidine, ciprofloxacin, diltiazem, dronedarone, erythromycin, fluconazole, grapefruit juice, Seville orange, isavuconazole, lefamulin, letermovir, netupitant, rauconazole, verapamil

The following medications and supplements are some of the moderate to strong inducers of CYP3A4. As described in the study protocol, concomitant use of moderate to strong CYP3A4 inducers is prohibited. This list should not be considered all-inclusive. Individual product labels should be reviewed for specific information on propensity to induce CYP3A4 for a specific compound.

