 - IWRS randomization stratum of "typical", but CRF Neuralgia type "atypical" (Demographics page)
- Prohibited non-study medications, procedures, or therapies defined as any of the following:
 - Standard of care Trigeminal Neuralgia medications with dose change or with start date < 4 weeks prior to randomization (see Section 4.4.1 for the definition of standard of care Trigeminal Neuralgia medication)
 - Carbamazepine taken during the Screening Period or afterward

- St. John's Wort taken up to 14 days prior to the Baseline Visit (randomization) or afterward
- Barbiturate-containing products (e.g. Fioricet, Fiorinal, butalbital, phenobarbital) taken up to 14 days prior to the Baseline Visit (randomization) or afterward
- Modafinil (PROVIGIL®) taken up to 14 days prior to the Baseline Visit (randomization) or afterward
- Butterbur root or extracts taken up to 14 days prior to the Baseline Visit (randomization) or afterward
- Ergotamine medications taken on ≥ 10 days per month on a regular basis for ≥ 3 months
- Narcotic medication, such as opioids, taken up to 2 days prior to the Baseline Visit or afterward
- Acetaminophen or acetaminophen containing products taken within 2 days before randomization.
- Use of acetaminophen during the Screening Period (3 to 14 days) or throughout the study at daily dosing levels of greater than 1000 mg/day
- Muscle relaxants (except baclofen) taken during the Screening Period or throughout the study
- Baclofen with start date < 8 weeks prior to randomization
- Strong CYP3A4 inhibitors taken during the Screening Period or throughout the study
- Strong CYP3A4 inducers taken during the Screening Period or throughout the study
- Strong inhibitors of the P-gp transporter taken during the Screening Period or throughout the study
- CGRP antagonists (biologic or small molecule) taken during the Screening Period or throughout the study

Note: Medications taken up to X days before a reference date or afterward are defined as those with medication start date or stop date \geq reference date $- X$. Refer to the Core SAP for additional details about prohibited non-study medications.

- DB study drug dosing issue, defined as any of the following subcategories (see Section 6.2.6):
 - DB study drug taken but not randomized
 - DB tablet count compliance < 80% from DB study drug start to later of last scheduled DBT Phase visit or DB study drug end
 - > 1 DB tablet taken on any 1 day
 - Incorrect DB study drug taken

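### Appendix 2 bars moderate CYP3A4 inhibitors and inducers, the Section 4.4 class rules bar only strong ones, and the SAP's deviation categories follow the narrower rule

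*Protocol*

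**What the plan says.** Protocol Section 4.4 sets class rules in two items. Item 10: "Concomitant use of strong CYP3A4 inhibitors with rimegepant is prohibited during the study". Item 11: "Concomitant use of strong CYP3A4 inducers with rimegepant is prohibited during the study". Both refer the reader to Appendix 2.

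Appendix 2 describes the rule differently. On inhibitors, it presents as the protocol's own rule that "concomitant use of moderate to strong CYP3A4 inhibitors is prohibited". On inducers: "As described in the study protocol, concomitant use of moderate to strong CYP3A4 inducers is prohibited". It then lists moderate agents of each kind by name, next to the strong ones.

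SAP Section 9.1 defines the relevant deviations for prohibited medication. Its CYP3A4 categories are "Strong CYP3A4 inhibitors taken during the Screening Period or throughout the study" and "Strong CYP3A4 inducers taken during the Screening Period or throughout the study". It has no category for moderate agents as a class. It refers to the Core SAP for further detail on prohibited medications.

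**The concern.** Items 10 and 11 rely on Appendix 2 to tell sites which drugs are meant, and Appendix 2 cites a protocol rule that the body does not contain. A site asked about diltiazem, ciprofloxacin or fluconazole finds no class prohibition in Section 4.4 and an explicit one in the appendix to which Section 4.4 points. Two sites can read the protocol carefully and treat the same drug differently.

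Three things follow.

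- **Safety and exposure.** The protocol restricts these drugs for use together with rimegepant. If the restriction varies by site, so may the handling of patients and their exposure to rimegepant.
- **Stopping of treatment.** Item 10 ties a consequence for rimegepant dosing to a required strong inhibitor. The documents do not say whether that consequence extends to the moderate inhibitors that Appendix 2 bars.
- **Reporting.** SAP 6.2.4.1 builds the relevant-deviation table from the categories in Section 9.1. Use that Appendix 2 calls prohibited therefore has no row of its own in that table.

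**Working it through.** No sample-size, power or error-rate figure is involved. The check compares the texts and counts the lists.

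**Step 1. The three places side by side.**

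| Class | Protocol 4.4 | Protocol Appendix 2 | SAP 9.1 |
|---|---|---|---|
| Strong CYP3A4 inhibitors | prohibited (item 10) | prohibited | category |
| Moderate CYP3A4 inhibitors | no class rule | prohibited | no category |
| Strong CYP3A4 inducers | prohibited (item 11) | prohibited | category |
| Moderate CYP3A4 inducers | no class rule | prohibited | no category |
| Strong P-gp inhibitors | prohibited (item 12) | prohibited | category |

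The P-gp row agrees in all three places, so the mismatch is confined to CYP3A4. The wider wording occurs in two separate sentences of Appendix 2, one for inhibitors and one for inducers, so a single slip in one sentence does not explain it.

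**Step 2. Entries listed as moderate in Appendix 2.** Inhibitors: 17. Inducers: 7. Total: 17 + 7 = 24.

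**Step 3. Entries caught by another rule.**
- Modafinil, a listed moderate inducer, is barred by name in Section 4.4 item 3 and counted by name in SAP 9.1.
- Dronedarone and verapamil, listed moderate inhibitors, are also on the Appendix 2 list of strong P-gp inhibitors. Item 12 bars that class and SAP 9.1 counts it.

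**Step 4. Entries left with conflicting status.** Inhibitors: 17 − 2 = 15. Inducers: 7 − 1 = 6. Total: 15 + 6 = 21, which equals 24 − 3.

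**Step 5. Where use of these 21 would be visible.** SAP 6.2.6.3 specifies double-blind concomitant-medication tables by preferred name, split by period and treatment, and a by-subject listing of concomitant medications. A recorded course of diltiazem would appear in both. The listing identifies medication types, but this SAP does not say that CYP3A4 class is one of them. In the relevant-deviation table the same course has no category.

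**The case against.** The strongest reply is that this is an ambiguity of scope with little effect on the results. Much of that stands, and it rules out several stronger readings that a reader might infer.

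- **That the two rules exclude each other.** They do not. Section 4.4 does not expressly permit moderate agents, and a site that avoids both classes complies with both texts. The fault is that a site following Section 4.4 alone would breach Appendix 2.
- **That moderate-agent use would go unseen.** It would not, as Step 5 shows. Only the deviation category and the flag are missing. A site could also document a case under Protocol 4.6, and it could reach the listing of significant deviations in SAP 6.2.4.2, but only if the site regarded it as a deviation, which is the matter in doubt.
- **That exposure becomes inconsistent within a patient across the two periods.** This does not fit the design: each sequence gives rimegepant in one double-blind period and placebo in the other. The exposure question in the crossover is between patients. The documents give no interaction size for moderate agents, so it cannot be quantified.
- **That 21 measures how much use to expect.** It counts list entries. Two are foods (grapefruit juice and Seville orange) that a medication record may miss. Lopinavir also appears, combined with ritonavir, among the strong inhibitors. Appendix 2 says its lists are not complete, and nothing shows how many patients took any listed agent.

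The Core SAP is a real limit. SAP Section 1 gives it primacy where it is directly referenced as applicable, and Section 9.1 does reference it on prohibited medications. It may add moderate agents. The categories printed in Section 9.1 nevertheless say strong.

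Practical weight is also reduced. SAP Section 1 reports early termination in 1Q2023 with only critical data to be analyzed, Section 5 says significance will not be evaluated, and the mITT definition in Section 4.1 does not exclude patients for prohibited medication. None of this removes the mismatch between Section 4.4 and Appendix 2.

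**Conclusion.** The inconsistency is real and holds at class level. For the 21 entries, Appendix 2 prohibits use, the Section 4.4 class rules do not, and the relevant-deviation table as specified in this SAP has no category. The consequence is possible site-to-site difference in how interacting drugs were restricted, with a bearing on patient safety and on rimegepant exposure between patients, and a deviation table that omits use which one part of the protocol calls prohibited. No efficacy estimate, power or error rate is altered by the wording itself.

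The conclusion takes the Appendix 2 lists at face value and assumes that the Core SAP adds no category for moderate agents. If it does, the SAP part falls away and the conflict inside the protocol remains. Which rule is clinically right is not judged here.

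**What to change.** Reconcile Section 4.4 items 10 and 11 with Appendix 2 so that they make one statement. The choice of rule is the sponsor's. The statement should also make clear which agents the dosing consequence in item 10 applies to. Then align the SAP 9.1 categories with it: a rule limited to strong agents leaves those categories as they are, and a wider rule needs a category for moderate agents.

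Since the study ended early, an amendment can no longer change site conduct. The action still open is in reporting:

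1. Flag moderate CYP3A4 agents by patient and period in the existing concomitant-medication listing.
2. State in the CSR which rule was applied when deviations were classified.
3. Check the Core SAP's text on prohibited medications and say whether it adds anything on this point.

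The cost is a sentence of protocol wording, at most one deviation category, and a flag on data already collected.
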